5.0 THERAPEUTIC/DIAGNOSTIC AGENTS

Sorafenib

Other names:	BAY 43-9006, Nexavar®		
Classification:	Kinase inhibitor		
Molecular weight	::Sorafenib tosylate: 637 Daltons; sorafenib (free base): 465 Daltons		
Mode of action:	Sorafenib is a potent inhibitor of VEGF-R, PDFG-R, c-raf, wild-type and mutant b-raf, Flt3, c-KIT and p38 α , a member of the MAPK family.		
Approximate Solubility:	0.19 mg/100 mL in 0.1 N HCl, 453 mg/100 mL in ethanol, 2971 mg/100mL in PEG 400		
How supplied:	BAY 43-9006 sorafenib 200 mg is supplied as round, biconvex, red-film- coated tablets, debossed with the 'Bayer cross' on one side and '200' on the other side. The tablets contain BAY 43-9006 tosylate equivalent to 200 mg of the free base BAY 43-9006, and the excipients croscarmellose sodium, microcrystalline cellulose, hypromellose, sodium lauryl sulfate, and magnesium stearate. The film-coat consists of hypromellose, polyethylene glycol, titanium dioxide and red iron oxide. The film coating has no effect on the rate of release of the active BAY 43-9006 tosylate.		

The study drug can be supplied as BAY 43-9006 soratenib 200 mg commercial tablets in bottles of 140 tablets with a product identification label affixed or as commercial Nexavar in bottles of 120 tablets.

IRB#: 09-016A(9)

Storage: Stability:	Store at controlled room temperature (15 -25 °C). Storage conditions should not exceed 25 °C. Stability studies are ongoing. The current shelf life is 24 months when
Stability.	stored at controlled room temperature.
Route of Administration:	Orally

Sorafenib is supplied as 200 mg tablets. The dose of sorafenib is 400 mg orally twice daily for 28 days (continuously). There is no planned interruption between treatment cycles. The cycle start date will coincide with the physician visit date. Because of the potential need for physician visit scheduling to vary (due to both physician and patient issues), to avoid violation of, and deviation from, the protocol, these visits may vary by up to one to fourteen (1-14) days.

Sorafenib will be taken in the outpatient setting on Days 1-28 of each 28-day cycle. Patients should swallow the tablet whole with approximately 250 ml (8 oz.) of water each morning and evening,. Sorafenib tablets may be crushed and administered via a feeding tube if necessary.

Sorafenib should be taken without food (1 hour before or 2 hours after eating). If it is taken with meals, patients will be instructed to take sorafenib with a low- to moderate-fat diet. A high fat meal causes a decrease in sorafenib absorption (a 29% decrease in sorafenib areaunder-the-curve (AUC) concentration and a 38% decrease in sorafenib maximum concentration (C_{max}) value).

Dose modifications for sorafenib are detailed in Section 11.5. Patients will be taken off sorafenib at disease progression.

Drug metabolism interactions: Sorafenib is primarily metabolized by two parallel pathways: CYP3A4-mediated oxidation and UGT1A9-mediated glucoronidation.³³ Pharmacokinetics analysis from previous clinical trials have not demonstrated any significant drug interactions when sorafenib was administered together with ketoconazole, a potent inhibitor of CYP3A4. Therefore, it is thought that sorafenib may be safely coadministered with substrates and inhibitors of CYP3A4, such as ketoconazole, itraconazole, fluconazole and ritonavir.³³ There is no clinical information on the effect of CYP3A4 inducers on the pharmacokinetics of sorafenib.³³ Inducers of CYP3A4 activity (e.g. rifampin, *Hypericum perforatum* also known as St. John's wort, phenytoin, carbamazepine, phenobarbital, and dexamethasone) may increase metabolism of sorafenib and thus decrease sorafenib plasma concentrations.

Concomitant administration of midazolam, dextromethorphan and omeprazole, which are substrates of cytochromes CYP3A4, CYP2D6 and CYP2C19, respectively, following four weeks of sorafenib administration did not significantly alter the exposure of these agents.³³

IRB#:09-016A(9)

This indicates that sorafenib is neither an inhibitor nor a clinically meaningful inducer of these cytochrome P450 isoenzymes.

Sorafenib is also known to inhibit CYP2C9 *in vitro*. Substrates of CYP2C9 include warfarin and digoxin. However, the previous phase III evaluation of sorafenib versus placebo for advanced renal cell carcinoma did not reveal a significant difference in PT/INR between both groups, suggesting that sorafenib may not have *in vivo* inhibitory activity against CYP2C9.³³ Nevertheless, routine monitoring of the PT/INR for patients on coumadin therapy is warranted.

Availability: Following submission and approval of the required regulatory documents, a supply of sorafenib may be ordered from Bayer Pharmaceuticals.

6.0 Criteria for subject eligibility

6.1 Subject Inclusion Criteria

To be included in the study, patients must fulfill all of the following inclusion criteria and not meet any of the exclusion criteria. Patients who give written informed consent prior to any study specific screening procedures proceed with the understanding that the patient has the right to withdraw from the study at any time, without prejudice.

- Patients must have histologically proven or cytologically confirmed esophageal cancer (squamous cell carcinoma or adenocarcinoma) or adenocarcinoma of the gastroesophageal (GE) junction documented at MSKCC.
- Metastatic disease measurable on a CT or MRI scan. Locally recurrent disease that is
 not amenable to potentially curative surgery or radiation therapy is also allowed.
 Lesions must be ≥10 mm in size. The primary tumor is not considered measurable
 disease. Recurrent or metastatic lesions within a prior radiation field are acceptable as
 long as disease has progressed in the radiation field by RECIST criteria. See Section
 12.2 for definition of measurable lesions. The same imaging modality performed at
 baseline (CT or MRI) will be repeated at subsequent imaging.
 - Patients are allowed to have a maximum of two prior chemotherapy regimens for metastatic disease. Patients are allowed to have a maximum of three prior regimens if they also previously received neoadjuvant/adjuvant chemotherapy or chemoradiotherapy. The last treatment must have been administered >3 weeks prior to initiation of therapy with sorafenib.
 - Pathologic tissue must be available for immunohistochemistry (IHC) staining for phosphorylated extracellular signal-regulated kinase (pERK). Both patients with and without pERK staining are eligible for treatment. Submission of slides and IHC

IRB#:09-016A(9)

testing for pERK may be done during the course of therapy and are not required prior to protocol therapy.

- Age ≥ 18 years.
- Life expectancy >3 months.
- Karnofsky performance status $\geq 60\%$.
- At baseline, patients must have normal organ and marrow function as defined:

Adequate bone marrow, liver and renal function as assessed by the following:

Hemoglobin \geq 9.0 g/dl

Absolute neutrophil count (ANC) \geq 1,500/mm³

Platelet count \geq 100,000/mm³

Total bilirubin \leq 1.5 times ULN

ALT and AST ≤ 2.5 times the ULN ($\leq 5 \times$ ULN for patients with liver involvement)

Creatinine \leq 1.5 times ULN

• Patients must have the ability to comprehend and willingness to sign an informed consent document.

6.2 Subject Exclusion Criteria

- Patients who have not recovered from adverse events related to therapy administered >3 weeks earlier. This does not include hemoglobin or other hematologic or laboratory criteria, as long as eligibility are met as outlined in 6.1.
- Patients may not be receiving any other investigational agents.
- Prior therapy with sorafenib-related compounds or compounds of similar biologic or chemical components, including compounds targeting VEGF, VEGF-R or RAF kinase.
- Uncontrolled intercurrent illness including, but not limited to, ongoing or active infection, greater than New York Heart Association (NYHA) Class II congestive heart failure, unstable or new onset angina pectoris or myocardial infarction within the past six months, unstable arrhythmia, or psychiatric illness/social situation, e.g. severe

[figure not shown]
Amended: 05/12/15

IRB#: 09-016A(9)

schizophrenia, that would limit compliance with study requirements. Patients with chronic arrhythmias, such as paroxysmal atrial fibrillation or paroxysmal supraventricular tachycardia, are eligible.

- Uncontrolled hypertension, defined as systolic blood pressure >150 mmHg or diastolic blood pressure >90 mmHg, despite optimal medical management.
- Thrombotic or embolic event, including cerebrovascular accident or transient ischemic attack within the past six months. Patients with prior deep vein thromboses or pulmonary emboli on a stable anticoagulation regimen will be eligible for enrollment.
- Any factor that would significantly interfere with the inability to consume or absorb an oral medication, e.g. severe nausea/vomiting not controlled by an aggressive antiemetic regimen, grade 3/4 dysphagia, extensive small bowel resection or active inflammatory bowel disease leading to chronic malabsorption. Patients with enteral feeding tubes are eligible as sorafenib can be crushed.
- Known human immunodeficiency virus (HIV) infection or chronic Hepatitis B or C infection.
- Patients with any other concurrent disease which, in the judgment of the investigator, would make the patient inappropriate for participation in the study.
- Patients who are taking St. John's wort or rifampin (as there may be drug-drug interactions with sorafenib; see Section 5.0 and 11.4).
- Patients with known brain metastases or meningeal carcinomatosis are excluded. Patients with neurological symptoms must undergo a CT scan/MRI of the brain to exclude brain metastasis.
- Pregnant women are excluded because sorafenib has the potential for teratogenic or abortifacient effects. Female patients must either not be of childbearing potential or must have a negative pregnancy test ≤ 7 days prior to treatment. Female patients are considered not of childbearing potential if they are surgically sterile (they have undergone a hysterectomy, bilateral tubal ligation or bilateral oophorectomy) or if they are post-menopausal. Men must use effective birth control if their partners are of child-bearing potential.
- No other malignancy is allowed except for adequately treated carcinoma in-situ of the cervix, superficial transitional cell carcinoma of the bladder or basal/squamous cell skin cancer. Other cancers are permissible if the patient has been disease free for ≥3 years.

IRB#:09-016A(9)

- Pulmonary hemorrhage/bleeding event
 > CTCAE Grade 2 within 4 weeks of first dose of study drug.
- Any other hemorrhage/bleeding event >CTCAE Grade 3 within 4 weeks of first dose of study drug.
- Serious non-healing wound, ulcer, or bone fracture.
- Evidence or history of bleeding diathesis or coagulopathy
- Major surgery, open biopsy or significant traumatic injury within 4 weeks of first study drug.
- Known or suspected allergy to sorafenib or any agent given in the course of this trial.

7.0 RECRUITMENT PLAN

This will be a single institution, phase II study. Patients with metastatic or recurrent esophageal and gastroesophageal (GE) junction cancer who are eligible will be identified for enrollment. No additional measures, e.g. advertisement, payment to patients, will be employed to recruit patients.

Inclusion of women and minorities

The investigators take due notice of the NIH policy concerning inclusion of women and minorities in clinical research populations. There will be no limitation with regards to race or gender.

Our institutional demographics for accrual of patients on esophageal and GE junction cancer trials reflect the national incidence of this disease. 10-15% of our patients have been women. African-American males (almost exclusively with esophageal squamous cell carcinoma) comprise 3-5% of patients treated on protocol. Given that our protocol accrual closely reflects the national incidence of this disease, no specific strategy will be undertaken to recruit women or persons of color on this trial.

This protocol/project does not include children because the number of children with esophageal and GE junction cancer is very small and because the majority are already accessed by a nation-wide pediatric cancer research network. This statement is based on exclusion 4b of the NIH Policy and Guidelines on the Inclusion of Children as Participants in Research Involving Human Subjects.

8.0 PRETREATMENT EVALUATION

To be completed within four weeks prior to study entry:

• A 12-lead electrocardiogram (ECG).

To be completed within two weeks prior to study entry:

Amended: 05/12/15

IRB#:09-016A(9)

- History and physical exam, including blood pressure, vitals, height, weight and performance status.
- Documentation of all measurable disease with a baseline computerized tomography (CT) or magnetic resonance imaging (MRI) scan of the chest and abdomen. All measurable lesions used to define response must be ≥10 mm in size. The primary tumor is excluded. Lesions within prior radiation fields are permitted as long as these lesions have documented progression in size.
- White blood cell (WBC) count, platelet count with automated differential.
- Comprehensive metabolic panel, including electrolytes, glucose, blood urea nitrogen (BUN), creatinine, lactate dehydrogenase (LDH), albumin, aspartate aminotransferase (AST or SGOT), alanine aminotransferase (ALT or SGPT), alkaline phosphatase, total bilirubin, total protein, prothrombin time (PT), international normalized ratio (INR) and partial thromboplastin time (PTT).
- Amylase/lipase.
- Serum pregnancy test, for all women of childbearing potential. Prior to study enrollment, women of childbearing potential (WOCP) must be advised of the importance of avoiding pregnancy during trial participation and the potential risk factors of an unintentional pregnancy. In addition, men enrolled on this study should understand the risk to any partner of childbearing potential and should practice an effective method of birth control.

All WOCP must have a negative pregnancy test ≤ 7 days prior to starting therapy.

In addition, all WOCP should be instructed to contact the Investigator immediately if they suspect they might be pregnant (e.g. late or missed period) at any time during study participation.

To be completed anytime prior to starting therapy

• Histological confirmation of metastatic esophageal or GE junction squamous cell carcinoma or adenocarcinoma prior to study enrollment. Patients without histological confirmation of recurrence or metastasis will undergo a biopsy to confirm recurrence, unless the risk of such a procedure outweighs the benefits of confirming recurrent disease.

9.0 TREATMENT/INTERVENTION PLAN

9.1 Agent administration

Amended: 05/12/15

IRB#:09-016A(9)

Treatment will be administered on an outpatient basis. Reported adverse events and potential risks are described in Section 11. Appropriate dose modifications are described in Section 11.5. Criteria for discontinuing treatment are listed in Section 13.

Sorafenib is supplied as 200 mg tablets. The starting dose of sorafenib is 400 mg orally twice daily for 28 days (continuously). There is no planned interruption between treatment cycles. The cycle start date will coincide with the physician visit date. Because of the potential need for physician visit scheduling to vary (due to both physician and patient issues), to avoid violation of, and deviation from, the protocol, physician visits may vary by up to one to fourteen (1-14) days from a strict 28 day schedule.

Sorafenib will be taken on Days 1-28 of each 28-day cycle. Patients shall swallow the tablet whole with approximately 250 ml (8 oz.) of water each morning and evening. Tablets may be crushed and administered via a feeding tube.

Sorafenib may be taken with or without food. If it is taken with meals, patients will be instructed to take sorafenib with a low- to moderate-fat diet.

A study diary will be completed by patients to ensure compliance with sorafenib (see Appendix A).

Patients will be required to take antacid therapy to reduce the potential for gastrointestinal bleeding. Allowable agents include but are not limited to ranitidine, omeprazole, carafate or similar agents.

9.2 Supportive care guidelines

- Patients should receive full supportive care, including transfusions of blood and blood products, antibiotics and anti-emetics. The reasons for treatment, dosage and dates of all supportive treatments should be recorded.
- Use of erythropoietin alfa (Epoetin alfa, Procrit®) and/or darbepoetin (Aranesp®) is permitted at the discretion of the treating physician based on standard MSKCC criteria.
- Patients who develop hand-foot reaction may receive topical emollients (such as Aquaphor®) or topical steroid or anti-histamine ointments, if appropriate.

IRB#: 09-016A(9)

	Pre-	Cycle 1 ¹		Cycle 2 & thereafter			Off-			
	study ^I	Wk	Wk	Wk	Wk	Wk	Wk	Wk	Wk	study
		1	2	3	4	1	2	3	4	
Sorafenib twice daily					Cont	inuous				
Informed consent	Х									
Demographics	Х									
Medicalhistory	Х									Х
Physicalexam ^k	Х	Х	Х	Х		Х				Х
Collect sorafenib diary						Х				Х
Vitals ^K	Х	Х	Х	Х		Х				Х
Blood pressure measurement ^{AK}	Х	Х	Х	Х		Х				Х
Height	Х									
Weight ^K	Х	Х	Х	Х		Х				Х
Performance status ^K	Х	Х	Х	Х		Х				Х
Concomitant medications ^K	Х	Х				Х				Х
CBC with diff, plts ^K	Х	Х	Х	Х		Х				Х
Comprehensive metabolic panel ^{C K}	Х	Х		Х		Х				Х
Amylase/lipase ^D	Х	Х		Х		Х				Х
PT/INR/PTT – not on Coumadin	Х									
PT/INR/PTT – on coumadin ^{EK}	Х	Х		Х		Х				Х
Adverse event evaluation				•	Cont	inuous				
Serumβ-HCG ^F	Х									
ECG	Х									
Radiographic tumor measurement ^{GK}	Х				Х				Х	
Tissue IHC for pERK ^H	Х									

10.0 EVALUATION DURING TREATMENT/INTERVENTION

A. Blood pressure measurement is required at baseline, weekly during Cycle #1 and then during Week #1 from Cycle #2 onwards. Patients will need to return to the clinic on weeks without scheduled physician evaluation for an RN evaluation or have their measurement obtained at their local physician's office or some other venue (e.g. patient-operated machine at a drug store, ambulatory blood pressure cuff, etc.) If measurements are not performed at MSKCC, patients will need to record their blood pressure and contact their study physician if it is elevated or, if normal, to provide the recordings to the study physician or nurse at their next scheduled clinic visit.

C. Comprising sodium, potassium, chloride, bicarbonate, BUN, creatinine, glucose, total bilirubin, total protein, AST, ALT, alkaline phosphatase.

D. Asymptomatic grade 3/4 hyperamylasemia and hyperlipasemia without evidence of pancreatitis were noted in 1% and 12% of patients respectively in the large phase III randomized trial of sorafenib in advanced renal cell carcinoma.

E. Because of a potential drug interaction with sorafenib, patients on chronic anticoagulation with coumadin will require periodic monitoring of their PT/INR every two weeks.

F. For women of childbearing potential (see section 8.0).

G. A CT or MRI will be obtained at baseline within two weeks of study enrollment. Repeat radiographic evaluation will be obtained after the first four weeks on study, at eight weeks, and then every eight weeks thereafter If a

IRB#: 09-016A(9)

complete response is achieved and maintained for 12 months, patients with complete response will then be required to repeat CT or MRI evaluation every 4 months up to 5 years post complete response status, then every 6 months thereafter. Patients with a partial/complete response require a confirmatory scan at least four weeks after the initial scan documenting response (see Section 12.5). The same imaging modality performed at baseline (CT or MRI) will be repeated at subsequent imaging.

H. Prior archived tissue must be obtained at anytime prior to enrollment or during protocol therapy for immunohistochemical staining for phosphorylated extracellular signal-regulated kinase (pERK).

I. If pre-treatment CBC, comprehensive metabolic panel and PT/INR/PTT are drawn within seven days of beginning therapy, they do not need to be re-drawn again during Cycle #1, Week #1.

J. Cycle start date will coincide with the physician visit date.

K. Because of the potential need for blood test, CT/MRI scan, and physician visit scheduling to vary (due to both physician and patient issues), to avoid violation of, and deviation from the protocol, blood tests, CT/MRI scans, and physician visits (including physical exam, vitals, blood pressure, weight, performance status, and concomitant medications) may vary by up to one to fourteen (1-14) days from a strict 28 day schedule.

Evaluations during treatment

Please note, because of the potential need for blood test, CT/MRI scans, and physician visit scheduling to vary (due to both physician and patient issues), to avoid violation of, and deviation from, the protocol, blood tests, CT/MRI scans and physician visits (which include physical exam, vitals, blood pressure, weight measurement, performance status assessment and concomitant medications) may vary up to one to fourteen (1-14)days from a strict 28 day schedule.

- A physical exam, vitals (including blood pressure) and weight measurement, and performance status assessment on Week 1, Week 2 and Week 3 of Cycle 1 and then on Week 1 of each Cycle thereafter.
- A CBC on Week 1, Week 2 and Week 3 of Cycle 1 and then on Week 1 of each Cycle thereafter.
- A comprehensive metabolic panel (CMP) on Week 1 and Week 3 of Cycle 1 and then on Week 1 of each Cycle thereafter.
- An amylase/lipase level on Week 1 and Week 3 of Cycle 1 and then on Week 1 of each Cycle thereafter.
- For patients on coumadin therapy, a PT/INR/PTT on Week 1 and Week 3 of Cycle 1 and then on Week 1 of each Cycle thereafter.
- Sorafenib diary to be collected on Week 1 of each new Cycle.
- A list of concomitant medications to be obtained on Week 1 of each new Cycle.
- A repeat CT or MRI of measurable disease after the first 4 weeks on study, at eight weeks, and then every 8 weeks thereafter. If a complete response is achieved and maintained for 12 months, patients with complete response will then be required to repeat CT or MRI evaluation every 4 months up to 5 years post complete response status, then every 6 months thereafter The same imaging modality performed at baseline (CT or MRI) will be repeated at subsequent imaging.

Evaluation at the end of study treatment:

Amended: 05/12/15

IRB#: 09-016A(9)

- A physical exam, vitals (including blood pressure) and weight measurement, and performance status assessment.
- A list of concomitant medications.
- Sorafenib diary to be collected.
- A CBC, CMP and amylase/lipase level. For patients on coumadin, a PT/INR/PTT level.

Immunohistochemistry for pERK

Phosphorylated extracellular signal-regulated kinase (pERK) determination through immunohistochemical (IHC) staining of prior paraffin stored tumor blocks or unstained slides. pERK determination may be pending at the time of protocol registration, with prior material submitted for IHC during the course of protocol therapy. The pERK status is not required for enrollment on the protocol. Studies will be performed at MSKCC.

Whenever possible, the most recent tumor biopsy/pathologic specimen prior to study enrollment will be used.

Paraffin-embedded tissue should be prepared by fixing tissues in 10% neutral buffered formalin. An optimal fixation time is 12 - 24 hours and should not exceed 48 hours. Slides should consist of a minimum of five unstained, positively charged microscope slides with $4 - 6 \mu m$ tissue sections, cut from a paraffin block. The slides should be prepared in a 37 - 42 °C water bath without gelatin. Only one $4 - 6 \mu m$ cut section is placed on each slide, opposite the frosted end, before the slides are allowed to air dry.

pERK tissue expression is assayed using a rabbit polyclonal antibody for pERK (phosphop44/42 mitogen activated protein kinase [Thr202/Tyr204]; Cell Signaling Technology Inc, Danvers, MA). A standard secondary biotinylated anti-mouse antibody and streptavidin horseradish peroxidase are then applied for visualization.

Briefly, the procedure involves: (1) Deparaffinization and rehydration of the tissues with xylene and graded alcohols; (2) Antigen unmasking by pretreatment with sodium citrate; (3) Incubation with primary antibody or negative control sera (non-specific mouse IgG); (4) Incubation with secondary biotinylated anti-mouse antibody; (5) Incubation with streptavidin horseradish peroxidase; (6) Incubation with substrate and chromogen (DAB) (7) Counterstaining the tissue with hematoxylin-eosin; (8) Mounting with an aqueous cover slip medium and; (9) Microscopy.

A positive control cell line (derived from a gastrointestinal stromal tumor cell line that expresses pERK) is included with each assay. Each specimen is reviewed after staining for the presence of tumor cells, the localization of pERK staining to the cell nuclei or the cytoplasm, the staining intensity and the proportion of tumor cells that stain positive. pERK staining is graded semi-quantitatively using a five-point scale: 0, no staining; 1+, weak; 2+, moderate; 3+ strong and; 4+, intense.

Amended: 05/12/15

IRB#: 09-016A(9)

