2.0 OBJECTIVES AND SCIENTIFIC AIMS

Primary objective:

To evaluate the 2-month progression-free survival (PFS) of sorafenib in patients with metastatic or recurrent esophageal and gastroesophageal (GE) junction cancer.

Secondary objectives:

a) To evaluate the overall response rate (partial response and complete response) of sorafenib.

b) To evaluate the tolerability and adverse event profile of sorafenib in this patient population.

c) To perform an exploratory analysis of differential response between squamous cell carcinoma and adenocarcinoma.

d) To evaluate phosphorylated extracellular signal-regulated kinase (pERK) expression in tumor tissue and correlate with tumor response.

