11.2 General toxicity profile

For the most recent safety update, refer to the Nexavar® Prescribing Information. The overall safety profile of sorafenib is based on 1,286 cancer patients, who received sorafenib as a single agent.³³

Table 11.2.1 will be used to determine the "expectedness" of adverse drug reactions used for reporting of adverse events to Regulatory Agencies. It is not a complete list of adverse events reported in clinical trials.

System Organ Class	Very Common	Common	Uncommon
	≥ 10%	≥1% to <10%	$\geq 0.1\%$ to < 1%
Infections and infestations			Folliculitis infection
Blood and lymphatic system	Lymphopenia	Leukopenia	
disorders		Neutropenia	
		Anemia	
		Thromboc ytopenia	
Immune system disorders			Hypersensitivity reactions
			(including skin reactions and
			urticaria)
Endocrine disorders			Hypothyroidism
Metabolism and nutrition	Hypophosphatemia	Anorexia	Hyponatremia
disorders			Dehydration
Psychiatric disorders		Depression	
Nervous system disorders		Peripheral sensory	Reversible posterior
		neuropathy	leukoencephalopathy*
Ear and labyrinth disorders		Tinnitus	
Cardiac disorders			Myocardial ischemia and
			infarction*
			Congestive heart failure*
Vascular disorders	Hemorrhage (including		Hypertensive crisis*
	gastrointestinal* and		
	respiratory tract* and		
	cerebral hemorrhage*)		
	Hypertension		

Table 11.2.1. Adverse drug reactions in patients in multiple clinical trials.

IRB#:09-016A(9)

* Events may have a life-threatening or fatal outcome. Such events are uncommon. **Palmar plantar erythrodysaethesia reaction

IRB PB

IRB#: 09-016A(9)

System Organ Class	Very Common ≥10%	Common ≥1% to <10%	Uncommon ≥ 0.1% to < 1%
Respiratory, thoracic and mediastinal disorders		Hoarseness	Rhinorrhea
Gastrointestinal disorders	Diarrhea Nausea Vomiting	Constipation Stomatitis (including dry mouth and glossodynea) Dyspepsia Dysphagia	Gastroesophageal reflux disease Pancreatitis Gastritis Gastrointestinal perforation*
Hepato-biliary disorders			Increase in bilirubin and jaundice
Skin and subcutaneous tissue disorders	Rash Alopecia Hand-foot reaction** Pruritis Erythema	Dry skin Dermatitis exfoliative Acne Skin desquamation	Eczema Erythema multiforme minor
Musculoskeletal, connective tissue and bone disorders		Arthralgia Myalgia	
Reproductive system and breast disorders		Erectile dysfunction	Gynecomastia

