11.3 Laboratory abnormalities

The following laboratory abnormalities were observed in the randomized phase III trial of sorafenib in patients with advanced renal cell carcinoma³³:

Elevated lipase and amylase: Elevated lipase and amylase levels were very commonly reported. Grade 3/4 lipase elevations occurred in 12% of patients in the sorafenib group compared to 7% of patients in the placebo group. Grade 3/4 amylase elevations were reported

IRB#:09-016A(9)

in 1% of patients in the sorafenib group compared to 3% of patients in the placebo group. Clinical pancreatitis was reported in 2 of 451 sorafenib treated patients (Grade 4) and 1 of 451 patients (Grade 2) in the placebo group.

Hypophosphatemia: Hypophosphatemia was a common laboratory finding, observed in 45% of sorafenib treated patients compared to 12% of placebo patients. Grade 3 hypophosphatemia (1-2 mg/dl) occurred in 13% of sorafenib-treated patients and 3% of patients in the placebo group. There were no cases of Grade 4 hypophosphatemia (< 1 mg/dl) reported in either sorafenib or placebo patients. The etiology of hypophosphatemia associated with sorafenib is not known.

Lymphopenia: Grade 3/4 lymphopenia was reported in 13% of sorafenib treated patients and 7% of placebo patients.

Neutropenia: Grade 3/4 neutropenia was reported in 5% of sorafenib treated patients and 2% of placebo patients.

Anemia: Anemia was observed in 44% of sorafenib-treated patients and 49% of placebo patients. Grade 3/4 anemia was reported in 2% of sorafenib-treated patients and 4% of placebo patients.

Thrombocytopenia: Thrombocytopenia was observed in 12% of sorafenib-treated patients and 5% of placebo patients. Grade 3/4 thrombocytopenia was reported in 1% of sorafenib-treated patients and 0% of placebo patients.

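### Hypophosphatemia is listed as very common on sorafenib, but no scheduled test measures phosphate, so the safety objective cannot give a valid rate for it

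*Combined protocol and SAP*

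**What the plan says.** Secondary objective b in Section 2.0 is "To evaluate the tolerability and adverse event profile of sorafenib in this patient population". Section 11.1 makes laboratory tests part of adverse-event monitoring, with the highest CTCAE grade recorded, and Section 14.0 says toxicities will be tabulated.

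Section 11.3 reports from the renal-cancer phase III trial: "Hypophosphatemia was a common laboratory finding, observed in 45% of sorafenib treated patients compared to 12% of placebo patients", and "Grade 3 hypophosphatemia (1-2 mg/dl) occurred in 13% of sorafenib-treated patients and 3% of patients in the placebo group". Table 11.2.1 puts "Hypophosphatemia" in the column for reactions seen in at least 10% of patients.

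The tests actually scheduled are these:

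- **Baseline (Section 8.0):** "Comprehensive metabolic panel, including electrolytes, glucose, blood urea nitrogen (BUN), creatinine, lactate dehydrogenase (LDH), albumin", followed by liver, protein and clotting tests. Phosphate is not named.
- **Panel content (Section 10.0, footnote C):** "Comprising sodium, potassium, chloride, bicarbonate, BUN, creatinine, glucose, total bilirubin, total protein, AST, ALT, alkaline phosphatase".
- **On treatment (Section 10.0):** "A comprehensive metabolic panel (CMP) on Week 1 and Week 3 of Cycle 1 and then on Week 1 of each Cycle thereafter", with blood counts, amylase/lipase and, for patients on coumadin, clotting tests.
- **End of treatment (Section 10.0):** "A CBC, CMP and amylase/lipase level", again with clotting tests for patients on coumadin.

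**The concern.** Section 11.3 describes grade 3 hypophosphatemia by a serum value of 1-2 mg/dl. It cannot be graded without an assay, and the calendar schedules none. What reaches the toxicity table then depends on which patients happened to have phosphate ordered for some other reason. The numerator is selectively ascertained, while the natural denominator is all 35 patients.

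At stake is one item in a descriptive secondary objective, but it is an item that the protocol itself singles out. A reader of the results could take a low count as evidence that the toxicity is less frequent in esophageal cancer, when the plan had no means of showing that.

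**Working it through.** **Step 1. Match each laboratory abnormality in Section 11.3 to a scheduled test.** The figures are the grade 3/4 rates quoted there (grade 3 for hypophosphatemia); the excess is sorafenib minus placebo, in percentage points.

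| Abnormality | Sorafenib | Placebo | Excess | Scheduled test |
|---|---|---|---|---|
| Hypophosphatemia | 13% | 3% | +10 | none |
| Lymphopenia | 13% | 7% | +6 | CBC with differential |
| Lipase | 12% | 7% | +5 | amylase/lipase |
| Neutropenia | 5% | 2% | +3 | CBC with differential |
| Thrombocytopenia | 1% | 0% | +1 | CBC with platelets |
| Anemia | 2% | 4% | -2 | CBC |
| Amylase | 1% | 3% | -2 | amylase/lipase |

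Hypophosphatemia is the only abnormality in the section without a test, and it has the largest excess over placebo.

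**Step 2. Check whether phosphate could be implied elsewhere.** Footnote C names 12 analytes as the content of the panel. The last, alkaline phosphatase, is an enzyme and does not measure serum phosphate. The Section 10.0 grid attaches footnote C to the pre-study panel as well, so the unspecified electrolytes of Section 8.0 are most naturally read as footnote C's sodium, potassium, chloride and bicarbonate. Scheduled phosphate measurements: 0.

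**Step 3. Expected cases if everyone were measured.** The 45% and 13% are cited without counts, so there is no formula to reproduce. With n = 35 (Section 4.2), and assuming that the renal-cancer rates carry over:

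- Any grade: 35 × 0.45 = 15.75, about 16.
- Grade 3: 35 × 0.13 = 4.55, so 4 to 5.

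**Step 4. Chance of at least one grade 3 case, 1 − (1 − p)^35, over a range of rates:**

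- p = 13%: 1 − 0.87^35 = 0.992.
- p = 6.5% (half): 1 − 0.935^35 = 0.905.
- p = 3% (placebo): 1 − 0.97^35 = 0.656.

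**Step 5. Expected recorded cases if unscheduled testing finds a fraction f of the true cases.** The documents give no value for f, so it is an assumption. Counts are 15.75f and 4.55f.

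| f | Any grade | Grade 3 |
|---|---|---|
| 0 | 0 (0%) | 0 (0%) |
| 10% | 1.6 (4.5%) | 0.5 (1.3%) |
| 25% | 3.9 (11%) | 1.1 (3.3%) |
| 50% | 7.9 (22.5%) | 2.3 (6.5%) |

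Between f = 25% and f = 50% the rate is understated four-fold to two-fold. If no case were recorded and the result were treated as 0/35, the exact 95% upper limit would be 1 − 0.025^(1/35) = 10.0%. That interval would exclude both 13% and 45%, although nobody had been tested on schedule.

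**The case against.** A reader might infer that the final table will show hypophosphatemia as nearly absent, and so make a false statement about tolerability. The documents do not support going that far. Section 14.0 prescribes no table format, so an unmeasured analyte could be left out or marked as not assessed. Adverse-event evaluation is continuous in the Section 10.0 grid, so investigators may order phosphate off schedule. By Step 5, a near-absent rate follows only if about 10% of cases or fewer are found.

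Three further points stand:

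- Section 11.6.3 makes a laboratory abnormality an adverse event only when it is considered clinically relevant or the investigator judges it so. Mild asymptomatic low phosphate might not be recorded even if measured, so the 16 any-grade cases are not the adverse-event count that testing alone would produce.
- The renal-cancer rates may not transfer. Median PFS on sorafenib there was 5.5 months (Section 3.5.3). The reference PFS here is 1.6-2.0 months (Section 4.2) and treatment stops at progression, so exposure could be shorter and cumulative incidence lower.
- The amylase/lipase comparison is imperfect. Section 11.3 mentions clinical pancreatitis alongside those enzymes, but gives no clinical sequela for phosphate and no grade 4 cases.

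These points limit the size of the effect and the claim about what would be printed. They do not supply the missing measurement. The investigator's judgment of relevance cannot be exercised on a value never obtained.

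**Conclusion.** The concern holds in this form: followed as written, the plan cannot estimate the incidence of a laboratory toxicity that it lists as very common. Any recorded rate would be too low by an amount that the trial's data could not reveal. The omission is certain from the text. The size is illustrative: the expected counts and the 99% rest on the renal-cancer rates carrying over, and the chance of at least one grade 3 case falls to 90% or 66% under the lower rates tried.

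The effect is confined to a descriptive secondary objective. The 2-month PFS test, the 35 patients and the decision rule of 22 or more are unaffected. It is worth correcting because the remedy is cheap.

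**What to change.** 1. Add serum phosphate to footnote C and name it in the Section 8.0 baseline panel. Run it on draws already scheduled: pre-study, Cycle 1 Weeks 1 and 3, Week 1 of each later cycle, and off-study. Naming it at baseline matters because footnote I lets a panel drawn within seven days of starting therapy replace the Cycle 1 Week 1 draw.
2. In Section 14.0, tabulate the worst graded phosphate value per patient, over patients with at least one on-treatment value, separately from adverse events judged clinically relevant under Section 11.6.3.
3. Have the sponsor reconcile Sections 10, 11.3 and 11.5. Table 11.5.4 ties dosing actions to grade 3 non-hematologic toxicity. Its footnote lists several laboratory exceptions but does not mention hypophosphatemia. Measured grade 3 values would come under that table, for 4 to 5 patients if the 13% rate applied. Which rule should apply is for the sponsor to settle.
4. If phosphate is not added, state in the plan and the report that hypophosphatemia was not systematically assessed and must not be read as absent.

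The direct cost is a small assay charge, with no new visit or procedure. The indirect cost is item 3: the new values could affect drug exposure, so the reconciliation should be done before testing starts.
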